15.8.2.4. Final Lead Placement Data Collection

Following fixation and once the final position of the lead is determined, collect a venous image of the final placement of the lead. A copy of the venous image will be submitted to Medtronic and kept on file at the center.

15.8.2.5. Pre-Hospital Discharge CRT System Testing and Programming

The following electrical testing will be performed using the implanted CRT-P or CRT-D device and the device programmer once the leads are connected to the CRT-P or CRT-D and pre-hospital discharge:

Lead Impedance

- Collect LV Lead Impedances using Vector Express on all vectors
- Perform a manual LV Lead Impedance Test for missing Vector Express values on vectors LV1 to RVcoil, LV2 to RVcoil, LV3 to RVcoil, LV4 to RVcoil or the final programmed vector
- Retain printouts for any manually tested vector at the site

Pacing Capture Thresholds (PCT)

- Perform PCTs at 0.5ms pulse width using Vector Express on all 16 vectors
- NOTE: A one time manual reprogramming the pulse width to 0.5ms will be required (Out of the box pulse width is set at 0.4ms)
- Perform a manual PCT test at 0.5ms pulse width for missing Vector Express values on vectors LV1 to RVcoil, LV2 to RVcoil, LV3 to RVcoil, LV4 to RVcoil or the final programmed vector
- Retain printouts for any manually tested vector at the site

Phrenic Nerve Stimulation (PNS)

- Test for presence of PNS at 8.0V at 0.5ms on final programmed vector
- NOTE: If PNS is present at 8.0V at 0.5ms, measure the PNS threshold at 0.5ms
- NOTE: PNS observed during this testing will not be considered an AE

Other Data Collection

Other data collected prior to hospital discharge following the implant includes;

- Rationale for selecting specific LV lead pacing vector for final programming
- Final device interrogation/save-to-media
- AE Assessment
- Study deviations
- Device deficiencies

15.9. 3 Months Post-Implant (remote or in office visit)

The 3 month scheduled follow-ups may be done remotely or inoffice. For remote visits, CareLink transmissions may substitute device interrogations. The following procedures will be completed and data will be collected at the 3 month Follow-up visit;

Lead Impedance

- Perform a manual LV Lead Impedance Test the final programmed vector
- Retain printouts for any manually tested vector at the site

Pacing Capture Thresholds (PCT)

- Perform PCTs at 0.5ms pulse width on the final programmed vector
- NOTE: A one time manual reprogramming the pulse width to 0.5ms will be required (Out of the box pulse width is set at 0.4ms)
- Perform a manual PCT test at 0.5ms pulse width on the final programmed vector
- Retain printouts for any manually tested vector at the site

Phrenic Nerve Stimulation (PNS) (in office visit only)

- Test for presence of PNS at 8.0V at 0.5ms on final programmed vector
- NOTE: If PNS is present at 8.0V at 0.5ms, measure the PNS threshold at 0.5ms
- NOTE: PNS observed during this testing will not be considered an AE

Other Data Collection

- NYHA classification
- Patient Global Assessment
- Rationale for selecting specific LV lead pacing vector for final programming
- Final device interrogation/save-to-media
- AE Assessment
- Study deviations
- Device deficiencies

15.10. 6 Months Post-Implant (in office visit)

The following procedures will be completed and data will be collected during the 6 month in office Follow-up visit.

Lead Impedance

- Collect LV Lead Impedances using Vector Express on all vectors
- Perform a manual LV Lead Impedance Test for missing Vector Express values on vectors LV1 to RVcoil, LV2 to RVcoil, LV3 to RVcoil, LV4 to RVcoil or the final programmed vector
- Retain printouts for any manually tested vector at the site

Pacing Capture Thresholds (PCT)

- Perform PCTs at 0.5ms pulse width using Vector Express on all 16 vectors
- NOTE: A one time manual reprogramming the pulse width to 0.5ms will be required (Out of the box pulse width is set at 0.4ms)
- Perform a manual PCT test at 0.5ms pulse width for missing Vector Express values on vectors LV1 to RVcoil, LV2 to RVcoil, LV3 to RVcoil, LV4 to RVcoil or the final programmed vector
- Retain printouts for any manually tested vector at the site

Phrenic Nerve Stimulation (PNS)

- Test for presence of PNS at 8.0V at 0.5ms on vectors LV1 to RVcoil, LV2 to RVcoil, LV3 to RVcoil, LV4 to RVcoil
- Test for presence of PNS at 8.0V at 0.5ms on final programmed vector
- NOTE: If at any tested vector PNS is present at 8.0V at 0.5ms, measure the PNS threshold at 0.5ms
- NOTE: PNS observed during this testing will not be considered an AE

Other Data Collection

- NYHA classification
- Patient Global Assessment
- Kansas City Cardiomyopathy Questionnaire (KCCQ)
- Rationale for selecting specific LV lead pacing vector for final programming
- Final device interrogation/save-to-media
- AE Assessment
- Study deviations
- Device deficiencies

15.11. 12 Months Post-Implant (in office visit)

The following procedures will be completed and data will be collected during the 12 month in office Follow-up visit.

Lead Impedance

- Collect LV Lead Impedances using Vector Express on all vectors
- Perform a manual LV Lead Impedance Test for missing Vector Express values on vectors LV1 to RVcoil, LV2 to RVcoil, LV3 to RVcoil, LV4 to RVcoil or the final programmed vector
- Retain printouts for any manually tested vector at the site

Pacing Capture Thresholds (PCT)

- Perform PCTs at 0.5ms pulse width using Vector Express on all 16 vectors
- NOTE: A one time manual reprogramming the pulse width to 0.5ms will be required (Out of the box pulse width is set at 0.4ms)
- Perform a manual PCT test at 0.5ms pulse width for missing Vector Express values on vectors LV1 to RVcoil, LV2 to RVcoil, LV3 to RVcoil, LV4 to RVcoil or the final programmed vector
- Retain printouts for any manually tested vector at the site

Phrenic Nerve Stimulation (PNS)

- Test for presence of PNS at 8.0V at 0.5ms on final programmed vector
- NOTE: If PNS is present at 8.0V at 0.5ms, measure the PNS threshold at 0.5ms
- NOTE: PNS observed during this testing will not be considered an AE

Other Data Collection

- NYHA classification
- Patient Global Assessment
- Kansas City Cardiomyopathy Questionnaire (KCCQ)
- Rationale for selecting specific LV lead pacing vector for final programming
- Final device interrogation/save-to-media
- AE Assessment
- Study deviations
- Device deficiencies

15.12. Recurring 6 Month Follow-ups

After the 12 Month Follow-Up visit, subjects will be seen every 6 months. These scheduled follow-ups are considered "Recurring 6 month follow-up visits". These scheduled follow-ups may be done remotely or inoffice. For remote visits, CareLink transmissions may substitute device interrogations. The following procedures will be completed during these visits:

Lead Impedance

- Perform a manual LV Lead Impedance Test for the final programmed vector
- Retain printouts for any manually tested vector at the site

Pacing Capture Thresholds (PCT)

- Perform PCTs at 0.5ms pulse width on the final programmed vector
- NOTE: A one time manual reprogramming the pulse width to 0.5ms will be required (Out of the box pulse width is set at 0.4ms)
- Perform a manual PCT test at 0.5ms pulse width on the final programmed vector
- Retain printouts for any manually tested vector at the site

Phrenic Nerve Stimulation (PNS) (in office visit only)

- Test for presence of PNS at 8.0V at 0.5ms on final programmed vector
- NOTE: If PNS is present at 8.0V at 0.5ms, measure the PNS threshold at 0.5ms
- NOTE: PNS observed during this testing will not be considered an AE

Other Data Collection

- NYHA classification
- Rationale for selecting specific LV lead pacing vector for final programming
- Final device interrogation/save-to-media
- AE Assessment
- Study deviations
- Device deficiencies

15.13. Device Interrogation/Save-to-Media

For the implant and follow-up visits, a final "Interrogate All" device interrogation file (.pdd) must be obtained and saved in a digital format (Save-to-Media). Store one copy of the save-to-media at the site and send a copy to Medtronic. Do not clear device data.

A device interrogation (final "Interrogate All") and Save-to-Media should also be completed at the time of study exit (prior to 6 month visit), a system modification (initial and final "Interrogate All"), and in the case of a death (where possible).

15.14. System Modifications

A system modification will be reported in the event the device and/or leads require invasive modification (e.g. generator or lead explant, generator or lead replacement, lead repositioning, etc.). In the event of a system modification, regardless of outcome of the modification, subjects should remain in the study when possible and the follow-up visit schedule for the subject will remain unchanged. For a system modification the following information/activities are required to be collected:

- Modification or replace/explant date
- Reason for modification
- Information on device or lead modified
- Information on any replacement device(s)
- Final device interrogation/save-to-media
- Study deviations
- AEs and device deficiencies (as applicable)

It is recommended that all explanted Medtronic products (device, leads, etc.) are returned to Medtronic for analysis per local process and when permissible by local laws and regulations.

In the event that subject has a re-attempt after a previous unsuccessful system modification, the subsequent attempt(s) must be reported via CRF as separate system modifications.

Attain Stability Quad MRI SureScan LV Lead (Model 4798) repositioned or replaced with another Attain Stability Quad MRI SureScan LV Lead (Model 4798)

If the Attain Stability Quad MRI SureScan LV Lead (Model 4798) is repositioned or replaced, the following LV lead electrical tests and data collection must be completed:

Lead Impedance

- Collect LV Lead Impedances using Vector Express on all vectors
- Perform a manual LV Lead Impedance Test for missing Vector Express values on vectors LV1 to RVcoil, LV2 to RVcoil, LV3 to RVcoil, LV4 to RVcoil or the final programmed vector
- NOTE: Retain printouts for any manually tested vector at the site

Pacing Capture Thresholds (PCT)

- Perform PCTs at 0.5ms pulse width using Vector Express on all 16 vectors
- NOTE: A one time manual reprogramming the pulse width to 0.5ms will be required (Out of the box pulse width is set at 0.4ms)
- Perform a manual PCT test at 0.5ms pulse width for missing Vector Express values on vectors LV1 to RVcoil, LV2 to RVcoil, LV3 to RVcoil, LV4 to RVcoil or the final programmed vector
- NOTE: Retain printouts for any manually tested vector at the site

Phrenic Nerve Stimulation (PNS)

- Test for presence of PNS at 8.0V at 0.5ms on final programmed vector
- NOTE: If PNS is present at 8.0V at 0.5ms, measure the PNS threshold at 0.5ms
- NOTE: PNS observed during this testing will not be considered an AE

Other Data Collection

- Record the reason why the final configuration was selected for final programming
- Record any programming changes to the LV lead apart from the LV lead pacing vector since the last visit and provide rationale for the change(s)

Attain Stability Quad MRI SureScan LV Lead (Model 4798) capped or explanted without replacement with another Attain Stability Quad MRI SureScan LV Lead (Model 4798)

If the Attain Stability Quad MRI SureScan LV Lead (Model 4798) is capped or explanted without replacement while the subject is in the study, subjects will continue to be followed per their original follow-up schedule for safety monitoring until study closure. LV lead electrical testing and interrogation files will not be required at follow-ups for subjects without the full protocol required system implanted.

Explant of the Attain Stability Quad MRI SureScan LV Lead (Model 4798) and the Medtronic CRT-P or CRT-D device without replacement with another Attain Stability Quad MRI SureScan LV Lead (Model 4798) and Medtronic CRT-P or CRT-D device

Subjects who have their Attain Stability Quad MRI SureScan LV Lead (Model 4798) and Medtronic CRT-P or CRT-D device explanted without replacement during a system modification procedure should be exited from the study as soon as all system related and/or system modification procedure related AEs are resolved. If no system or procedure related AEs are present at the conclusion of such a system modification procedure, the subject should be exited immediately.

Medtronic CRT-P or CRT-D device explanted without replacement, Attain Stability Quad MRI SureScan LV Lead (Model 4798) remains implanted

If the Medtronic CRT-P or CRT-D device is explanted and a replacement device will be implanted, all attempts should be made to replace with another Medtronic CRT-P or CRT-D device. In the event that an explanted Medtronic CRT-P or CRT-D device cannot be replaced with a new Medtronic CRT-P or CRT-D device, subjects who still have an Attain Stability Quad MRI SureScan LV Lead (Model 4798) implanted will continue to be followed for safety monitoring in person per their original follow-up schedule until study closure. Events related to the Attain Stability Quad MRI SureScan LV Lead (Model 4798) should be reported. Left ventricular lead electrical testing will not be required at follow-ups for subjects without the full protocol required system implanted. In an event that a second Attain Stability Quad MRI SureScan LV Lead (Model 4798) was implanted as a result of an Attain Stability Quad MRI SureScan LV Lead (Model 4798) related complication, the subject will be followed for safety, however the second implanted Attain Stability Quad MRI SureScan LV Lead (Model 4798) will not be included for the analyses of study objectives except reportable system related adverse events.

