15.16.2. Investigator Withdraws Subject

No subjects should be withdrawn by investigators unless compelling medical justification is present. It is recommended investigators discuss any withdrawals with the study sponsor prior to exiting subjects. If

an Investigator withdrawal is necessary, the following data should be collected prior to subject withdrawal if possible:

- Report the reason for subject withdrawal
- Final device interrogation/save-to-media
- Study deviations
- AEs and device deficiencies (as applicable)

The following are reasons for investigator-initiated subject withdrawal;

Medical Necessity

A subject may be exited from the study if an investigator feels it is necessary to withdraw the subject from the study due to a medical condition or other reason. In such cases, the subject will be notified and provided an explanation regarding the reasons for the study exit.

Explant of Medtronic CRT-P or CRT-D Device and Attain Stability Quad MRI SureScan LV Lead (Model 4798)

Subjects in which the Attain Stability Quad MRI SureScan LV Lead (Model 4798) and the Medtronic CRT-P or CRT-D device are explanted without replacement (i.e., subject no longer has a Medtronic CRT-P or CRT-D device and an Attain Stability Quad MRI SureScan LV Lead (Model 4798) implanted) shall be exited from the study (refer to Section 15.8.2.2). Subjects exposed to an Attain Stability Quad MRI SureScan LV Lead (Model 4798) through a lead attempt must be followed through at least one month or until all implant related AEs (system-, and/or procedure-related) have resolved or are unresolved with no further actions planned. Subjects who have either an Attain Stability Quad MRI SureScan LV Lead (Model 4798) (active or not active) or a Medtronic CRT-P or CRT-D device implanted will continued to be followed for safety until study completion.

Attain Stability Quad MRI SureScan LV Lead (Model 4798) Not Implanted

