Subjects that are not anticipated to have an implant attempt (e.g. do not meet inclusion/exclusion criteria) must be exited from the study. Subjects that have a CRT system implant attempt, but who do not have an Attain Stability Quad MRI SureScan LV Lead (Model 4798) attempted (See Section 15.8.2.2 for definition) will be exited from the study following their procedure unless an Attain Stability Quad MRI SureScan LV Lead (Model 4798) attempt is scheduled. If this attempt is more than 30 days from the baseline assessment, verification of the baseline data must be completed prior to a subsequent implant attempt.

Subjects with an unsuccessful Attain Stability Quad MRI SureScan LV Lead (Model 4798) implant attempt will be followed at pre hospital discharge and one month unless there are ongoing implant related AEs (system- and/or procedure related), in which case they will be followed beyond one month until the implant related (i.e., system-, and/or procedure related) AEs have been resolved or are considered unresolved with no further actions planned. The subjects may be followed via a clinic visit or by phone contact. In geographies where the Attain Stability Quad MRI SureScan LV Lead (Model 4798) is market-released, subjects will be exited from the study after the assessment of implant procedure or CRT system related AEs if the initial attempt of one Attain Stability Quad MRI SureScan LV Lead (Model 4798) model was unsuccessful. The subject may undergo implant attempts with any market released LV lead that provides the best benefit to the patient, but data collection on these subsequent attempts will not be required as these subjects will be considered exited from the study.

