15.14. System Modifications

A system modification will be reported in the event the device and/or leads require invasive modification (e.g. generator or lead explant, generator or lead replacement, lead repositioning, etc.). In the event of a system modification, regardless of outcome of the modification, subjects should remain in the study

when possible and the follow-up visit schedule for the subject will remain unchanged. For a system modification the following information/activities are required to be collected:

- Modification or replace/explant date
- Reason for modification
- Information on device or lead modified
- Information on any replacement device(s)
- Final device interrogation/save-to-media
- Study deviations
- AEs and device deficiencies (as applicable)

It is recommended that all explanted Medtronic products (device, leads, etc.) are returned to Medtronic for analysis per local process and when permissible by local laws and regulations.

In the event that subject has a re-attempt after a previous unsuccessful system modification, the subsequent attempt(s) must be reported via CRF as separate system modifications.

Attain Stability Quad MRI SureScan LV Lead (Model 4798) repositioned or replaced with another Attain Stability Quad MRI SureScan LV Lead (Model 4798)

If the Attain Stability Quad MRI SureScan LV Lead (Model 4798) is repositioned or replaced, the following LV lead electrical tests and data collection must be completed:

Lead Impedance

- Obtain LV Lead Impedance Test for the final programmed vector
- Perform a manual test for a missing value
- NOTE: Retain printouts at the site

Pacing Capture Thresholds (PCT)

- Obtain a PCT at 0.5ms pulse width using Vector Express on the final programmed vector
- Perform a manual test for a missing value
- NOTE: A one time manual reprogramming the pulse width to 0.5ms will be required (Out of the box pulse width is set at 0.4ms)
- NOTE: Retain printouts at the site

Phrenic Nerve Stimulation (PNS)

- Test for presence of PNS at 8.0V at 0.5ms on final programmed vector
- NOTE: If PNS is present at 8.0V at 0.5ms, measure the PNS threshold at 0.5ms
- NOTE: PNS observed during this testing will not be considered an AE

Other Data Collection

- Record the reason why the final configuration was selected for final programming
- Record any programming changes to the LV lead apart from the LV lead pacing vector since the last visit and provide rationale for the change(s)

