15.16.2. Investigator Withdraws Subject

No subjects should be withdrawn by investigators unless compelling medical justification is present. It is recommended investigators discuss any withdrawals with the study sponsor prior to exiting subjects. If

an Investigator withdrawal is necessary, the following data should be collected prior to subject withdrawal if possible:

- Report the reason for subject withdrawal
- Final device interrogation/save-to-media
- Study deviations
- AEs and device deficiencies (as applicable)

The following are reasons for investigator-initiated subject withdrawal;

Medical Necessity

A subject may be exited from the study if an investigator feels it is necessary to withdraw the subject from the study due to a medical condition or other reason. In such cases, the subject will be notified and provided an explanation regarding the reasons for the study exit.

Explant of Medtronic CRT-P or CRT-D Device and Attain Stability Quad MRI SureScan LV Lead (Model 4798)

Subjects in which the Attain Stability Quad MRI SureScan LV Lead (Model 4798) and the Medtronic CRT-P or CRT-D device are explanted without replacement (i.e., subject no longer has a Medtronic CRT-P or CRT-D device and an Attain Stability Quad MRI SureScan LV Lead (Model 4798) implanted) shall be exited from the study (refer to Section 15.8.2.2). Subjects exposed to an Attain Stability Quad MRI SureScan LV Lead (Model 4798) through a lead attempt must be followed through at least one month or until all implant related AEs (system-, and/or procedure-related) have resolved or are unresolved with no further actions planned. Subjects who have either an Attain Stability Quad MRI SureScan LV Lead (Model 4798) (active or not active) or a Medtronic CRT-P or CRT-D device implanted will continued to be followed for safety until study completion.

Attain Stability Quad MRI SureScan LV Lead (Model 4798) Not Implanted

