Subjects that are not anticipated to have an implant attempt (e.g. do not meet inclusion/exclusion criteria) must be exited from the study. Subjects that have a CRT system implant attempt, but who do not have an Attain Stability Quad MRI SureScan LV Lead (Model 4798) attempted (See Section 15.8.2.2 for definition) will be exited from the study following their procedure unless an Attain Stability Quad MRI SureScan LV Lead (Model 4798) attempt is scheduled. If this attempt is more than 30 days from the baseline assessment, verification of the baseline data must be completed prior to a subsequent implant attempt.

Subjects with an unsuccessful Attain Stability Quad MRI SureScan LV Lead (Model 4798) implant attempt will be followed at pre hospital discharge and one month unless there are ongoing implant related AEs (system- and/or procedure related), in which case they will be followed beyond one month until the implant related (i.e., system-, and/or procedure related) AEs have been resolved or are considered unresolved with no further actions planned. The subjects may be followed via a clinic visit or by phone contact. In geographies where the Attain Stability Quad MRI SureScan LV Lead (Model 4798) is market-released, subjects will be exited from the study after the assessment of implant procedure or CRT system related AEs if the initial attempt of one Attain Stability Quad MRI SureScan LV Lead (Model 4798) model was unsuccessful. The subject may undergo implant attempts with any market released LV lead that provides the best benefit to the patient, but data collection on these subsequent attempts will not be required as these subjects will be considered exited from the study.

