19.1. Primary Objectives

19.1.1. Primary Safety Objective

Objective

The Attain Stability Quad MRI SureScan LV Lead (Model 4798) will be considered safe if the probability of subjects free of Model 4798 lead-related complications at 6 months post-implant is greater than 87% (i.e., the lower bound of a one-sided 97.5% confidence interval must be greater than 87%).

Hypothesis:

$$H_0: S_{(6\text{-month})} \leq 87\%$$

$$H_1: S_{(6\text{-month})} > 87\%$$

where $S_{6\text{-month}}$ is the probability that a subject remains free from Model 4798 lead related complications through 6 months since implant.

Endpoint Justification

The study primary safety endpoint is Attain Stability Quad MRI SureScan LV Lead (Model 4798) related complications. All reported system and procedure-related AEs will be reviewed by an event review committee for LV lead relatedness and severity (see Section 18.1).

Utilizing lead related complication free survival probability to evaluate lead safety performance is widely accepted across cardiac device manufacturers and in the medical literature. Current already market-released Quadripolar LV lead 6-month safety performance is summarized in Table 16. The population performance of the Attain Stability Quad MRI SureScan LV Lead (Model 4798) is expected to be similar to the Medtronic Attain Performa Model 4298 lead.

Table 16: Safety Performance of Market Released Quadripolar Lead

	Medtronic Attain Performa	St. Jude Medical Quartet²²	Boston Scientific ACUITY X4²³
6-month LV Lead Complication Free Survival Probability Estimate	Model 4298 (Canted): 96.0% Model 4398 (Straight): 98.8% Model 4598 (S-shape): 96.2%	96% at 3 months	Straight: 96.5% Spiral: 98.5%

[figure not shown]
Statistical Analysis Methods

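### Sections 15.14 and 15.16.2 give conflicting study-exit rules after full explant, and complications that first appear after the explant may have no required collection route

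*Protocol*

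**What the plan says.** The rules below read the same in both versions of the protocol in the file.

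- **15.14, full explant.** When the lead and the CRT device are both removed and not replaced, the subject "should be exited from the study as soon as all system related and/or system modification procedure related AEs are resolved". For the subject with no open event the text adds: "If no system or procedure related AEs are present at the conclusion of such a system modification procedure, the subject should be exited immediately".
- **15.16.2, explant of device and lead.** Such subjects are to be exited, but those exposed to the lead "through a lead attempt must be followed through at least one month or until all implant related AEs" have resolved or need no further action. No start date is given for the month.
- **15.14, partial explant.** If only the lead is capped or explanted, or only the device is removed, the subject stays on the original schedule for safety until study closure.
- **15.14, opening.** It says that "regardless of outcome of the modification, subjects should remain in the study", qualified by the words that follow: when possible.
- **15.15 and 17.1.3.** After exit no further study visits are required. For exits before the 6-month visit, efforts to continue follow-up concern system- or procedure-related events that are still unresolved.
- **19.1.1.** The primary safety quantity is "the probability that a subject remains free from Model 4798 lead related complications through 6 months since implant".

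**The concern.** A site facing a full explant in the first month cannot follow both rules: one ends participation when the procedure ends, the other asks for a month or for resolution of events. For a later explant, whether any post-explant observation is owed depends on a start date that the text leaves out.

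Events after an explant are within scope. Table 12 counts as procedure related an event tied to surgical modification of the system. Section 16 lists vein damage, perforation, tamponade and pericardial effusion among the lead's potential risks, and these need not be evident when the procedure ends. Secondary Objective 2 reports fixation-related complications as a group of their own. At stake is the completeness of safety collection in subjects who have had a helix-fixated lead removed. Any loss can only lower the complication count.

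**Working it through.** The plan states no figure on this point, so there is none to reproduce. The check sets the rules side by side and then bounds the effect.

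**Step 1: what each rule gives a fully explanted subject.**

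| Situation | 15.14 | 15.16.2, month from attempt | 15.16.2, month from explant |
|---|---|---|---|
| Event open at end of procedure | stays until resolved | stays at least until the month ends or the event resolves | same |
| No open event, explant within a month of the attempt | exits the same day | remainder of the month | one month |
| No open event, explant later | exits the same day | nothing further | one month |

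Section 15.8.2.2 defines an attempt as any introduction of the lead into the body, so every implanted subject was exposed through an attempt and falls under 15.16.2. That clause speaks of implant-related events, which suggests that the month runs from the attempt. Its alternative (a month, or resolution) can also be read as already met when no event exists. The gap is therefore the whole no-open-event branch under 15.14, and the last row under the middle reading of 15.16.2.

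**Step 2: is there another route after exit?** 17.1.3 continues only unresolved events. 15.15 requires no visits after exit, and its recommendation to delay exit concerns ongoing events. Complaint reporting under 17.5 is stated not to be part of the study. None of these requires collection of a new event.

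**Step 3: possible number of events.** The protocol gives neither a rate of full explant nor a rate of delayed events, so both ranges are assumptions. Per 400 subjects at 6 months:

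- full explants at 0.5% to 2%: 400 × 0.005 = 2 to 400 × 0.02 = 8
- delayed event in 2% to 10% of these: 2 × 0.02 = 0.04 to 8 × 0.10 = 0.8
- as a share of subjects, at most 0.8 / 400 = 0.2 percentage points

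**Step 4: room in the primary safety test.** The criterion is a one-sided 97.5% lower bound above 87%. With x events in N subjects and no censoring, S = 1 − x/N, and the log-log bound is S^exp(1.96 × se), where se = √(x / (N(N − x))) / |ln S|.

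- N = 400, x = 38: S = 0.905, se = 0.0162 / 0.0998 = 0.162, bound = 0.905^1.374 = 0.872, which passes. At x = 39 the bound is 0.869, which fails.
- N = 170: 13 events pass and 14 do not.
- The exact binomial bound gives the same limits, 38 and 13.

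At the planning value of 94% complication-free, expected events are 0.06 × 400 = 24 and 0.06 × 170 = 10.2. Adding the upper end of Step 3 gives 24.8 against a limit of 38. At N = 170, 170 × 0.02 × 0.10 = 0.34, giving about 10.5 against 13.

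**The case against.** A reader might infer from 15.14 that delayed explant complications are never collected. The documents do not support that. Section 15.16.2 covers the same situation and asks for at least a month or resolution of events, and a subject with an event still open at the end of the procedure stays in under 15.14 itself. What remains is the conflict, the missing start date, and the branch with no open event.

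A reader might also size the problem from implant-site infection in the pooled history (44 of 3,246, or 1.36%, about 6 of 471). That is the wrong group. A subject explanted for infection will usually still have that event open and so is not exited at once.

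A contrast with failed attempts is tempting, because 15.16.2 says that subjects with an unsuccessful "implant attempt will be followed at pre hospital discharge and one month". That rule is not uniform. Where the lead is market-released, the same section exits such subjects after assessment of events, and 15.8.2.2 gives no fixed month. The firmer comparison is within 15.14, with subjects who lose only the lead or only the device.

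Three further points stand in the plan's favour:

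- The opening of 15.14 carries its own qualifier, so a specific rule for subjects with nothing left implanted is an exception to it and not a contradiction.
- The primary analysis counts the first lead-related complication. Where such a complication led to the explant, the subject has already had the event.
- A delayed event counts toward the primary endpoint only if the CEC finds it related to the LV lead.

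These limit the effect on the primary endpoint. They do not reconcile the two exit rules.

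**Conclusion.** The point holds as a contradiction between 15.14 and 15.16.2, with an undefined start for the one-month period and, on two of the possible readings, no required collection of complications that first appear after a full explant. The size is small: roughly 0.04 to 0.8 events per 400 subjects, on assumed rates of full explant (0.5% to 2%) and delayed event (2% to 10%) that the documents neither give nor exclude. Not every missed event would be a first, CEC-confirmed lead complication within 183 days, so the effect on the primary estimate is smaller still.

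The loss runs in one direction, toward a safer-looking lead. A reader might infer that the primary safety result is materially biased, but the margin in Step 4, computed without censoring, does not support that. This is a gap in safety collection that is worth closing because the correction is easy.

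**What to change.** Replace the two passages with one study-exit rule for subjects whose lead and device are both explanted without replacement, stated in one of 15.14 and 15.16.2 and cross-referenced from the other. State the date from which any minimum follow-up runs, and remove the immediate-exit sentence so that adverse-event collection does not end on the day of explant. The length and form of that follow-up are for the sponsor to set. The change concerns study exit and event collection, not care after explant.

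The cost is a wording change in two sections and, depending on the rule chosen, brief contact with very few subjects (2 to 8 per 400 on the assumed rates).
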